13.6.1	Internal Data and Safety Monitoring Committee.....	20
14	DATA HANDLING AND RECORD KEEPING.....	20
14.1	Confidentiality.....	20
14.2	Source Documents.....	20
14.3	Case Report Forms.....	20
14.4	Records Retention.....	20
15	AUDITING, AND INSPECTING.....	21
15.1	Auditing and Inspecting.....	21
16	ETHICAL CONSIDERATIONS.....	21
17	STUDY FINANCES.....	21
17.1	Funding Source.....	21
17.2	Conflict of Interest.....	21
18	PUBLICATION PLAN.....	21
19	REFERENCES.....	22

2 List of Tables

Table 1: Long-Term Clinical Studies with Clenbuterol.....	6
Table 2: Other Clinical Studies Using Clenbuterol.....	7
Table 3: Testing Schedule.....	15
Table 4: Power Percentage and Standard Deviation Assuming 25 Patients.....	16

3 List of Figures

4 List of Abbreviations

Adverse Event (AE)
 ALS Functional Rating Scale (ALSFRS-R)
 Alanine Aminotransferase (ALT)
 Amyotrophic Lateral Sclerosis (ALS)
 Aspartate Aminotransferase (AST)
 Creatine Kinase (CK)
 Enzyme Replacement Therapy (ERT)
 Forced Vital Capacity (FVC)
 Institutional Review Board (IRB)
 Late-Onset Pompe Disease (LOPD)
 Left Ventricular Assist Devices (LVAD)
 Left Ventricular (LV)
 Maximum Voluntary Ventilation (MVV)
 Microgram (mcg)
 Not Applicable (NA)

5 Study Summary

Title	A Clinical Investigation of the Safety and Efficacy of Clenbuterol on Motor Function in Individuals with Amyotrophic Lateral Sclerosis
Short Title	Clenbuterol in ALS
Protocol Number	NA
Phase	Phase ½
Methodology	Single arm
Study Duration	24 weeks
Study Center(s)	Single-center
Objectives	The goals are to determine safety and efficacy with regard to motor function of oral clenbuterol in subjects with ALS
Number of Subjects	25
Diagnosis and Main Inclusion Criteria	
 1. Diagnosis of ALS according to the El Escorial criteria 2. Age: 18+ years at enrollment.
Study Product, Dose, Route, Regimen	Clenbuterol (Spiropent): 40 to 80 mcgs BID per oral (up to 160 mcg per day maximum)
Duration of administration	24 weeks
Reference therapy	Standard of care at baseline
Statistical Methodology	The critical test of treatment efficacy will be the comparison of the ALSFRS-R slope during treatment to the estimated pre-treatment slope.

6 Introduction

This document is a protocol for a human research study. This study is to be conducted according to US and international standards of Good Clinical Practice (FDA Title 21 part 312 and International Conference on Harmonization guidelines), applicable government regulations and Institutional research policies and procedures.

6.1 Background

Amyotrophic lateral sclerosis (ALS) is a progressive neurodegenerative disease that lacks effective treatment, proceeding to respiratory failure and premature death for affected individuals. The neuropathy of ALS involves both upper motor neurons (UMN) and lower motor neurons (LMN) with critical secondary muscle involvement (KINSLEY AND SIDDIQUE 1993). UMN signs include hyperreflexia, Babinski sign, increased muscle tone, and weakness. LMN signs include weakness, muscle wasting, hyporeflexia, muscle cramps, and fasciculations. Affected individuals typically present with either asymmetric weakness of the extremities (stumbling or poor handgrip), termed “limb onset” or bulbar findings (dysarthria, dysphagia). Limb onset is more frequent than bulbar onset. Once it begins, the weakness progresses, ultimately leading to total disability and dependence and shortened survival. The mean age of onset is 56 years in individuals with no known family history and 46 years in individuals with more than one affected family member (familial ALS or FALS). Average disease duration is about three years, but it can vary significantly. Death usually results from compromise of the respiratory muscles. Multiple confirmed genetic and suspected environmental causes have been described (KINSLEY AND SIDDIQUE 1993). Current ALS treatments have little effect on disease progression and are mainly directed at optimizing quality of life (Oskarsson and Staff 2018).

The lack of effective therapy to reverse weakness or arrest ALS disease progression represents a critical unmet medical need. Clenbuterol’s ability to promote muscle hypertrophy and improve muscle function make it an attractive option for filling this need. Clenbuterol has been shown to stimulate muscle hypertrophy through inducing expression of insulin-like growth factor (Igf) -1 and Igf-2 and their receptors (MATSUMOTO *et al.* 2006).

Clenbuterol is a selective β_2 agonist used for the treatment of asthma in Europe with a well-established record of safety. In asthmatic patients with exercise induced bronchospasm a dose of 20 mcg of clenbuterol given intravenously over 3-4 minutes resulted in negligible cardiac effects (DEL BONO *et al.* 1979). Subjects with asthma given 80 mcg of clenbuterol had a mild increase in heart rate, but no arrhythmia or significant electrocardiographic changes, tremor and headache has also been noted in asthma patients as well (WHITSETT *et al.* 1981). Multiple other studies in asthmatics and patients with chronic airway obstruction, found none or very mild AE (PASOTTI *et al.* 1979; TSCHAN *et al.* 1979; DI GIOACCHINO *et al.* 1987). These and other studies reassure us regarding the potential use of clenbuterol in ALS (BIRKS *et al.* 2006; KAMALAKKANNAN *et al.* 2008).

Clenbuterol has been well tolerated and had beneficial muscle effects in a Phase I/II clinical trial (160 mcg/day) that enrolled patients with late-onset Pompe disease who were previously treated with ERT (KOEBERL *et al.* 2018). Similar dosages have increased muscle strength or increased muscle mass in other studies. Patients with chronic heart failure developed increased lean muscle

mass after taking clenbuterol at 80 mcg/day for 12 weeks (KAMALAKKANNAN *et al.* 2008). A small group of patients with Duchenne muscular dystrophy developed increased power and volume of well-preserved muscle following 18 months of taking clenbuterol, 30-40 mcg/day (OYA *et al.* 2001). Adverse events (AEs) associated with clenbuterol may include tremor, muscle cramps, nervousness, palpitations, tachycardia, and headache (Table 1), and are typically well-tolerated. These studies demonstrated the benefits of clenbuterol's effects on muscle, and its safety and tolerability in a variety of conditions other than ALS.

A previous small open-label pilot trial of clenbuterol in patients with ALS showed very promising results (SORARU *et al.* 2006). Sixteen patients with ALS were started on 60 mcg/day, and fourteen completed 6 months of treatment. Significant improvements in limb muscle strength and forced vital capacity (FVC) occurred in these patients, and a functional measure called the ALS functional rating scale score was stable over the course of the trial. Improvements and stability on these recognized ALS outcome measures are not typical of the natural history of this disease. Again, clenbuterol was found to be safe and well-tolerated (Table 1). The dramatically positive results of this pilot trial need to be replicated.

Table 1: Long-Term Clinical Studies with Clenbuterol

Study	Study Design	Number of Subjects	Dosage and Regimen	Adverse Events
(DI GIOACCHINO et al. 1987)	Open label study of clenbuterol in exercise induced asthma	14 patients	20 mcg bid for 60 days	Small increase in heart rate
(ISHIKO et al. 2000)	Randomized study of clenbuterol and physiological therapy (PT) in stress incontinence	61 patients assigned to three groups A-clenbuterol only B- PT only C - both	20 mcg bid for 12 weeks in 41 patients (group A and C)	1) Two patients with headache 2) One patient with mild hepatopathy 3) One patient with rash 4) One patient with numbness
(SORARU et al. 2006)	6 month open label dosing in patients with ALS already on riluzole	16 patients	20 mcg TID for 6 months	Tremor, nervousness, cramps, fasciculations (details not provided)
(KAMALAKKANNAN et al. 2008)	Single site, randomized, double blind placebo controlled in subjects with class 2 or 3 congestive heart failure	19 subjects -- 10 placebo 9 clenbuterol	20 mcg BID, increased to 40 mcg BID after 7 days – 12 weeks total	1) Two clenbuterol subjects withdrew, one with asymptomatic ventricular tachycardia, and one with muscle cramps without elevated CK 2) Six clenbuterol and two placebo subjects with muscle cramps 3) CK elevated in 5

				subjects on clenbuterol, and in 4 on placebo 4) Tremors in 5 subjects on clenbuterol and two on placebo
(KOEBERL et al. 2018)	52 week double-blind, placebo controlled, prospective study in LOPD patients stably treated with ERT for >1 year	13 randomized, 11 completed	40 mcg for 1 week, 40 mcg BID for 5 weeks, 80 mcg AM + 40 mcg PM for 1 week, 80 mcg BID for 40 weeks	4 subjects with tremor 4 subjects with insomnia 4 subjects with muscle spasms

6.2 Investigational Agent

ACTIONS AND MODE OR MECHANISMS OF ACTIONS

Clenbuterol is a broncholytic agent which acts through selective stimulation of the β_2 -receptors. It differs from other β_2 -specific sympathomimetics by its low dose, long biological half-life and rapid and complete absorption by oral administration. It has no significant effects on β_1 -cardiac receptors.

PHARMACOLOGY

Pharmacokinetics: Invasion half-life of clenbuterol is 1 hour, and the distribution corresponds to an open two compartment model with a side-compartment. Elimination from plasma takes place in 2 phases, the half-life of the α -phase being 1 hour and that of β -phase 34 hours. Elimination is primarily renal (87% after 168 hours) 43% of clenbuterol is recovered unchanged in the urine. Dose intervals of 12 hours suffice to maintain a plasma level. Five metabolites have been found in humans.

INDICATIONS

Prophylaxis and therapy of bronchospasm in bronchial asthma, acute and chronic bronchitis associated with emphysema.

CONTRAINDICATIONS

Thyrotoxicosis, idiopathic hypertrophic subvalvular aortic stenosis, tachycardia, tachyarrhythmia. Known sensitivity to sympathomimetic amines.

SIDE EFFECTS/ADVERSE REACTIONS

Side effects rarely occur at the recommended doses. Some patients could have, at the beginning of the treatment, tremor, nervousness, extrasystoles, tachycardia, palpitations, vertigo, anxiety, headache and nausea. In these cases the dose should be reduced.

PRECAUTIONS/WARNINGS

Warnings: Although animal studies have shown no teratogenic effect, clenbuterol should not be given during the first three months of pregnancy.

Precautions: Care must be exercised when additional sympathomimetic agents or IMAO drugs are administered. Clenbuterol should be used with caution in patients with hypertension, coronary heart disease, hyperthyroidism and diabetes. Caution should be used when treating patients with recent cardiac infarction.

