8.2 Primary Study Endpoints

The primary endpoint is safety of clenbuterol at 80 mcg BID. Adverse and serious AEs will be systematically gathered as described in section 8 below.

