9.2 Exclusion Criteria

1. Concurrent illness or laboratory abnormalities that could confound the measurement of ALS progression or interfere with the ability to complete the study.
2. Taking any investigational study drug within 30 days of screening or five half-lives of the prior agent.
3. No previous exposure to clenbuterol.
4. Pregnancy
5. Clinically relevant EKG abnormality (arrhythmia, cardiomyopathy)
6. Tachycardia (resting heart rate greater than 100 beats per minute)
7. History of seizure disorder
8. Hyperthyroidism
9. Pheochromocytoma
10. Pregnancy
11. Have any other co-morbid conditions that in the opinion of the study investigator, places the participant at increased risk of complications, interferes with study participation or compliance, or confounds study objectives
12. History of hypersensitivity to β 2-agonist drugs such as albuterol, levalbuterol (Xopenex), bitolterol (Tornalate), pirbuterol (Maxair), terbutaline, salmeterol (Serevent).
13. The use of the following concomitant meds is prohibited during the study:
 - i. diuretics (furosemide, Lasix)
 - ii. digoxin (digitalis, Lanoxin);
 - iii. β -blockers such as atenolol (Tenormin), metoprolol (Lopressor), and propranolol (Inderal);
 - iv. tricyclic antidepressants such as amitriptyline (Elavil, Etrafon), doxepin (Sinequan), imipramine (Janimine, Tofranil), and nortriptyline (Pamelor);
 - v. MAO inhibitors such as isocarboxazid (Marplan), phenelzine (Nardil), rasagiline (Azilect), selegiline (Eldepryl, Emsam), or tranylcypromine (Parnate); or
 - vi. other bronchodilators such as albuterol (Ventolin), levalbuterol (Xopenex), bitolterol (Tornalate), pirbuterol (Maxair), terbutaline (Brethine, Bricanyl), salmeterol (Serevent), isoetherine (Bronkometer), metaproterenol (Alupent, Metaprel), or isoproterenol (Isuprel Mistometer).

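### Exclusion 12 is limited to beta-2 agonists and so is narrower than the contraindication in section 6.2, which covers sympathomimetic amines generally (minor)

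*Combined protocol and SAP*

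**What the plan says.** Section 6.2 (Investigational Agent), under contraindications, reads: "Thyrotoxicosis, idiopathic hypertrophic subvalvular aortic stenosis, tachycardia, tachyarrhythmia. Known sensitivity to sympathomimetic amines". The final entry is not restricted to any subgroup of sympathomimetics. Earlier in the same section, clenbuterol is distinguished from other beta-2 "specific sympathomimetics by its low dose, long biological half-life and rapid and complete absorption by oral administration".

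Section 9.2 has one criterion about a past reaction to a drug, item 12. It excludes a history of hypersensitivity to beta-2 "agonist drugs such as albuterol, levalbuterol (Xopenex), bitolterol (Tornalate), pirbuterol (Maxair), terbutaline, salmeterol (Serevent").

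Two more general items might be thought to help. Item 1 excludes "Concurrent illness or laboratory abnormalities that could confound the measurement of ALS progression or interfere with the ability to complete the study". Item 11 begins: "Have any other co-morbid conditions that in the opinion of the study investigator, places the participant at increased risk of complications". It goes on to interference with participation or compliance and to confounding of the study objectives.

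Section 8.2 states: "The primary endpoint is safety of clenbuterol at 80 mcg BID".

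**The concern.** A contraindication is the protocol's own statement that a person should not receive the drug. The eligibility list is where that statement takes effect. If the list is narrower than the contraindication, staff who follow it faithfully can enrol someone whom section 6.2 would keep out.

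The timing adds some weight. Table 3 puts consent, medical history and drug dispensing in a single Screening/Baseline visit at Week 0, and section 8.1 starts the drug at that visit. The next scheduled contact is a telephone call at Week 1, and the next visit in person is at Week 4. Section 6.2 gives a terminal half-life of 34 hours, so exposure does not end promptly when dosing stops. The entry criteria are therefore the main written safeguard before the first dose, in a study whose primary endpoint is safety.

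**Working it through.** No figure in the plan bears on this point and no arithmetic applies. The check compares the texts.

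**Step 1: breadth of the contraindication.** Section 6.2 refers to sympathomimetic amines without qualification. Its pharmacology text speaks of beta-2-specific sympathomimetics, which makes beta-2 agents a subset of sympathomimetics. On the document's own wording, the contraindicated class is wider than beta-2 agonists.

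**Step 2: breadth of item 12.** The criterion is confined to beta-2 agonists. Its list is open, but the examples extend it within that class and not beyond it. There is also a difference of degree: section 6.2 says sensitivity, and item 12 says hypersensitivity.

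**Step 3: whether another criterion covers the remainder.**

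| Place | What it addresses | Reaches a past reaction to a non-beta-2 sympathomimetic? |
|---|---|---|
| 9.1, all 12 inclusion items | Diagnosis, function, background ALS drugs, swallowing, age, consent, contraception, pregnancy test | No |
| 9.2 item 1 | Current illness or laboratory findings that confound ALS measurement or prevent completion | No |
| 9.2 item 3 | Previous exposure to clenbuterol itself | No |
| 9.2 item 11 | Co-morbid conditions, in the investigator's opinion | Possibly, by discretion; a past drug reaction in someone otherwise well is not plainly a co-morbid condition |
| 9.2 item 13 and section 10.6 | Drugs that may not be taken during the study | No; they restrict current use, not past sensitivity |

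The other items in 9.2 (recent investigational drugs, pregnancy, EKG abnormality, resting heart rate, seizures, thyroid disease, pheochromocytoma) do not concern drug reactions.

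**Step 4: whether the narrowing looks deliberate.** Section 9.2 gives no reason for it. On several other points 9.2 is stricter than 6.2. Section 6.2 warns about the first three months of pregnancy, and 9.2 excludes pregnancy outright. Section 6.2 asks for care with MAO inhibitors, and item 13 prohibits them. This makes an oversight more likely than a choice, but the documents do not settle it.

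**Result.** Item 12 covers part of the contraindicated class. The remainder is left to item 11 at the investigator's discretion, or to the investigator's own reading of section 6.2.

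**The case against.** The best case against the point concerns its weight. Clenbuterol is a selective beta-2 agonist, and item 12 already covers that class with an open list. What remains is a person sensitive only to some other sympathomimetic amine. The documents name no such drug and give no cross-reactivity data, case or prevalence. An investigator could reasonably apply item 11, or simply consult section 6.2 of the same protocol, and this is a single-centre study in which medical history is reviewed before dosing. Treatment starts at 40 mcg once daily for a week, with a safety call at Week 1, and the investigator may withdraw a subject. All of this stands and is why the point is minor. It does not remove the mismatch: discretion narrows the gap without closing it, and later monitoring does not replace an entry criterion.

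Three stronger readings are tempting and are not supported.

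- *That contraindicated patients will be enrolled, or that the safety result is compromised.* The documents give nothing from which to estimate how often this would occur or what harm would follow.
- *That item 5 leaves a second gap, for hypertrophic subvalvular aortic stenosis with an unremarkable EKG.* Item 5 reads "Clinically relevant EKG abnormality (arrhythmia, cardiomyopathy"). If cardiomyopathy is read as a diagnosis, the patient is already excluded. If an EKG finding is required, a known stenosis is squarely a co-morbid condition under item 11. Arrhythmia stands in the same parenthesis, so the stenosis cannot be called uncovered while tachyarrhythmia is called covered.
- *That section 6.2 means allergic-type reactions only, so mild expected effects should be carved out.* Section 6.2 does not define sensitivity. Its side-effect text, "tremor, nervousness, extrasystoles, tachycardia, palpitations, vertigo, anxiety, headache and nausea. In these cases the dose should be reduced", does not separate the two ideas cleanly, because tachycardia is also a contraindication. A carve-out could leave item 12 still narrower than 6.2.

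**Conclusion.** The mismatch is real: a contraindication stated for sympathomimetic amines is carried into the entry criteria only for beta-2 agonists, and no other criterion clearly covers the rest. It is a minor patient-safety alignment. The number of patients affected is unknown and probably small. Sample size, power and the planned analyses do not change.

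The conclusion rests on two readings: that section 6.2 uses sympathomimetic amines in the general sense its own text implies, and that item 11, being discretionary and worded for co-morbid conditions, does not clearly cover a past drug reaction. If the sponsor confirms that item 11 is meant to be used this way, what is left is a matter of clarity.

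**What to change.** Reword item 12 of section 9.2 to match section 6.2, for example: *Known sensitivity or hypersensitivity to sympathomimetic amines, including beta-2 agonist drugs such as [existing list].* Ask about it at the medical history that section 11 already requires before study drug starts. If the narrower wording is intended, a sentence in 9.2 giving the reason would suffice.

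The cost is one phrase in a protocol amendment, with no new procedure or visit. The downside is a possible small loss of eligible patients at a single centre planning 25 subjects, since the wording also takes in sensitivity short of hypersensitivity. The documents give no prevalence, so the size of that loss cannot be stated.

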6.3 Preclinical Data

Teng and colleagues investigated the effect of clenbuterol upon longevity in a transgenic murine model of familial ALS (TENG et al. 2006). Clenbuterol treated mice demonstrated improved neuromuscular function through better Rotarod performance, slower disease progression, and reduced loss of lumbar motor neurons and body weight. These benefits are attributable to clenbuterol's induction of muscle Igf-1 expression and the associated muscle hypertrophy (MATSUMOTO et al. 2006), because the expression of Igf-1 with gene therapy in muscle has also improved muscle function and survival in mice with ALS (KASPAR et al. 2003). These data suggest that clenbuterol will have beneficial effects both through muscle hypertrophy and neuroprotection in ALS. The main symptoms of ALS stem from muscle weakness, and respiratory muscle weakness is the main cause of mortality.

6.4 Dose Rationale and Risk/Benefits

The selected dose (80 mcg BID) is based upon the experience with the long-term administration of clenbuterol, specifically the beneficial muscle effects in a Phase I/II clinical trial that enrolled patients with late-onset Pompe disease who were previously treated with ERT (KOEBERL et al. 2018).

The potential benefits outweigh anticipated risks for daily clenbuterol administration in patients with ALS. Clenbuterol treatment has been associated with specific AEs that may include tremor, muscle cramps, nervousness, and headache (Table 1), as observed in our Phase I/II study in patients with Pompe disease (KOEBERL et al. 2018). Cardiovascular adverse effects of clenbuterol may include palpitations associated with an increase in heart rate. However use of clenbuterol in conservative doses (up to 720 mcg/day) is well tolerated. In a pilot study of patients with congestive heart failure (CHF), clenbuterol was given at 40 mcg twice daily for 12 weeks in 19 patients (n=10 clenbuterol, n=9 placebo) with chronic heart failure in addition to their standard CHF therapy. *The drug was well tolerated and there were no serious AEs in that study.* Only two patients required discontinuation of study drug (one due to asymptomatic slow ventricular tachycardia seen on a 24-hour electrocardiogram and the other due to muscle cramps). Muscle cramps occurred in 6 clenbuterol subjects; only one subject required dose reduction. CK was elevated in 6 clenbuterol subjects (range of peak CK was 300-664 mg/dl, normal range 51-294 mg/dl) and mild tremors were reported in five subjects. No subjects required dose reduction due to elevation of CK or tremors in that study. (KAMALAKKANNAN et al. 2008) In our study in Pompe disease two subjects required dose reduction to 120 mcg from 160 mcg twice daily, due to minor AEs that resolved subsequently (KOEBERL et al. 2018).

In a pilot study of patients with congestive heart failure (CHF), clenbuterol was given at 40 mcg BID per oral for 12 weeks in 19 patients (n=10 clenbuterol, n=9 placebo) with chronic heart failure in addition to their standard CHF therapy. The drug was well tolerated and there were no serious adverse effects in any of the study subjects. Only two patients required discontinuation of study drug (one due to asymptomatic slow ventricular tachycardia seen on a 24- hour electrocardiogram and the other due to muscle cramps). Muscle cramps occurred in 6 clenbuterol subjects; only one subject required dose reduction. CK was elevated in 6 clenbuterol subjects (range of peak CK300-664 mg/dl, normal range 51-294 mg/dl) and mild tremors were reported in five subjects. No subjects required dose reduction due to elevation of CK or tremors (KAMALAKKANNAN *et al.* 2008).

Other studies generated data about the use of clenbuterol in patients with cardiac disease (Table 2). Clenbuterol in high doses (up to 2100 mcg/day) has been administered to 19 patients with end-stage HF supported with an LVAD, without significant arrhythmia or AE (YACOUB 2001; BIRKS *et al.* 2006). A study of clenbuterol in seven patients with implanted left ventricular assist devices (LVAD), a maximal dose of 720 mcg per day was given over 3 months. All seven patients were treated with and continued a maximum tolerated dose of metoprolol prior to initiation of clenbuterol. This dose of clenbuterol was well tolerated in all subjects. Serum creatine kinase (CK) was elevated in four subjects on clenbuterol, peak range (314-1497mg/dl). Mild tremors were seen in three subjects; mild muscle cramps were reported in four. No dose reduction was required for AE and there were no arrhythmic events (GEORGE *et al.* 2006). In another study of 15 patients with LVAD in heart failure were treated with clenbuterol. The first stage of treatment was four drugs, lisinopril, carvedilol, spironolactone, and losartan. The second phase of treatment was initiated when carvedilol was replaced with bisoprolol, and clenbuterol was started at a dose of 40 mcg three times daily and titrated to a maximal dose of 700 mcg TID (2100 mcg/day). Mild tremor was seen in all patients, muscle cramps in 3, but without elevated CK, and 1 patient had diaphoresis (BIRKS *et al.* 2006). A prospective study in 2011 looked again at this same pharmacological therapy of 20 patients with continuous flow LVAD with heart failure again showing that clenbuterol was well tolerated, with 4 patients developing muscle cramps and 2 developing mild tremor (BIRKS *et al.* 2011).

Clenbuterol has also been shown to be well tolerated when used to treat urinary incontinence in Germany and Japan (Table 2). In a controlled double blind study of 39 patients with motor urge incontinence, 20 were treated with 10 mcg clenbuterol three times a day and the other 19 were treated with flavoxate hydrochloride for 6 weeks. Adverse events consisted of 4 patients with trembling fingers and tachycardia, 3 patients with nervousness and 1 patient stopped due to a drug interaction with an alpha stimulating, antihypertensive drug, clonidine which caused dizziness (GRUNEBERGER 1984). In a comparison study of three groups of women all with stress incontinence, Group A got clenbuterol only, Group B got physiological therapy and Group C got both. Clenbuterol was given at a dose of 20 mcg twice daily for 12 weeks. Adverse events consisted of 2 patients with headache, 1 patient with mild hepatopathy, 1 patient with rash and 1 patient with numbness (ISHIKO *et al.* 2000).

Table 2: Other Clinical Studies Using Clenbuterol

Heart Failure Subjects (Reference)	Study Design	Number of Subjects	Dosage and Regimen	AEs
(BIRKS et al. 2006)	All received LV assist device and were in severe heart failure, primary pharm regiment and the secondary regiment of clenbuterol	15 subjects	40 mcg BID, titrated up to 40 mcg TID then titrated up to 700 mcg TID	Mild tremor in all 4 with muscle cramps without elevated CK Diaphoresis in 1
(GEORGE et al. 2006)	All with LV assist devices with heart failure	7 subjects	Started at 40 mcg TID titrated up to 720 mcg a day over 6 weeks, 12 weeks of total treatment	4 with elevated CPK, all had increases in CPK 3 with tremors 4 with muscle cramps
(BIRKS et al. 2011)	All received LV assist device and were in severe heart failure, primary pharm regiment and the secondary regiment of clenbuterol	20 subjects	16 of the 20 made it to stage 2 to receive clenbuterol started at 40 mcg BID and increased to 700 mcg TID	4 with muscle cramps 2 with mild tremors 2 with ventricular tachycardia that was not clenbuterol
Asthma/ Chronic Airway obstruction Subjects (Reference)	Study Design	Number of Subjects	Dosage and Regimen	AEs
(WHITSETT et al. 1981)	Single oral doses of clenbuterol compared to placebo, randomized double blind crossover in subjects with reversible obstructive airway disease	13 subjects, 10 finished study	Multiple single oral doses in 40, 60 and 80 mcg	Tremor and headache

(TSCHAN et al. 1979)	Dose response study of clenbuterol in subjects with obstructive lung disease	12 subjects	6,12, 24 and 48 mcg given qd for 4 days	No side effects noted
(PASOTTI et al. 1979)	Double blind comparison of clenbuterol and salbutamol in subjects with asthma	30 subjects	15 clenbuterol 30 mcg BID for 3days and then 20 mcg BID	No side effects noted
(DI GIOACCHINO et al. 1987)	Open label study of clenbuterol in exercise induced asthma	14 subjects	20 mcg BID for 60 days	Small increase in heart rate
(BRUSASCO et al. 1980)	Single blind cross over study comparing clenbuterol and terbutaline in subjects with chronic airway obstruction	16 subjects	20 to 30 mcg TID for 2 weeks	5 with tremors
(DEL BONO et al. 1979)	Single blind placebo controlled cross over study comparing IV clenbuterol and IV terbutaline in asthmatic subjects	9 subjects	20 mcg daily by IV for 4 days	No adverse reactions were observed with clenbuterol

Incontinence Subjects (Reference)	Study Design	Number of Subjects	Dosage and Regimen	AEs
(GRUNEBERGER 1984)	Controlled double blind study of Flavoxate vs Clenbuterol in motor urge incontinence	39 subjects total 20 subjects in Clenbuterol arm and 19 in Flavoxate arm	20 subjects treated for 6 weeks with 10 mcg clenbuterol three times a day	4 with trembling fingers and tachycardia 3 with nervousness 1 subject stopped due to a drug interaction with an alpha stimulating, antihypertensive drug, clonidine that caused dizziness
(ISHIKO et al. 2000)	Randomized study of clenbuterol and physiological therapy (PT) in stress incontinence	61 subjects assigned to three groups A-clenbuterol only B- PT only C - both	20 mcg BID for 12 weeks in 41 subjects (group A and C)	2 with headache 1 with mild hepatopathy 1 with rash 1 with numbness

7 Study Objectives

Primary Objective

To assess the safety and tolerability of clenbuterol in subjects with ALS

Secondary Objective

To assess the efficacy of clenbuterol with regard to motor function in subjects with ALS

8 Study Design

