13.6 Medical Monitoring

13.6.1 Internal Data and Safety Monitoring Committee

The study will be monitored throughout the trial by a Data and Safety Monitoring Committee (DSMB) consisting of a 4 Duke University School of Medicine faculty members who are unaffiliated with the study. The DSMB will convene during the study at approximately 6 month intervals to review summaries of accrual and enrollment information, results for EKGs and PFTs, and safety (AEs, withdrawal from study). The DSMB will provide summaries to the PI's. Safety will be monitored on an ongoing basis as descriptions of SAEs will be communicated to the DSMB Chair within 24 hours of their occurrence.

14 Data Handling and Record Keeping

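### Only SAEs reach the DSMB Chair within 24 hours, so a ventricular arrhythmia or drug-stopping adverse event graded non-serious could wait up to about 26 weeks for DSMB review

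*Combined protocol and SAP*

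**What the plan says.** **Routes to the DSMB.** Section 13.6.1 sets two. The fast one is for serious events: "descriptions of SAEs will be communicated to the DSMB Chair within 24 hours of their occurrence". The slow one is the periodic meeting: "The DSMB will convene during the study at approximately 6 month intervals". EKG results, lung function results, adverse events and withdrawals are reviewed at those meetings.

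**What counts as serious.** Section 13.1.2 (repeated in 13.5.2) lists six criteria. Stopping study drug is not among them. The last criterion, the important medical event, is described in terms of what may endanger the subject or call for intervention. Its examples are overdose or abuse, seizure and bronchospasm; arrhythmia is not mentioned. Under section 13.1.1 an abnormal test that leads to withdrawal is an adverse event, with nothing to make it serious.

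**Other outside bodies.** Section 13.3.1 sends SAEs to the IRB within 10 working days. Section 13.3.2 sends the FDA serious, unexpected, related events within 15 calendar days, and fatal or life-threatening ones within 7.

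**The background evidence.** Section 6.4 says of a cited study in chronic heart failure: "The drug was well tolerated and there were no serious AEs in that study". It then reports that two subjects stopped study drug, "one due to asymptomatic slow ventricular tachycardia seen on a 24-hour electrocardiogram" and the other because of cramps. The section gives the same account a second time.

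**The concern.** Safety at 80 mcg BID is the primary endpoint (section 8.2), and the trial is single-arm and open-label. The DSMB members are unaffiliated with the study, so they are its independent check on emerging harm. An adverse event that makes a subject stop the drug is among the most informative early safety signals, and so is a ventricular arrhythmia on a beta-agonist. Yet how soon the DSMB hears of either depends entirely on one grading decision. Two reasonable investigators could grade the same asymptomatic EKG finding differently, and the time to DSMB awareness would move from one day to as much as half a year. In that time other subjects could pass through the Week 6 dose increase (section 8.1), and the affected subject's 24 weeks could end, without the DSMB having seen the event.

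**Working it through.** The plan has no power, sample size or alpha figure on this point. The check is a reading of the reporting rules, followed by arithmetic on the delay.

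**1. Is there another fast route?** Take a ventricular arrhythmia, or an adverse event that stops the drug, graded non-serious.
- 24-hour notice to the DSMB Chair: no, SAEs only (13.6.1).
- IRB report: no, SAEs only (13.3.1).
- FDA report: no, serious, fatal or life-threatening events only (13.3.2).
- Periodic DSMB meeting: yes (13.6.1).
- Investigator: yes. Adverse events are sought at every contact (13.2), EKGs are done at Weeks 4, 12 and 24 (section 11), and the investigator may take a subject off study (9.4).

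The gap is therefore in DSMB review, not in clinical awareness.

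**2. Length of the wait.** Inputs: meeting interval of 6 months (13.6.1) and treatment of 24 weeks (8.1).
- Interval L = 6 × 30.4375 / 7 = 26.1 weeks. This is the maximum wait.
- Average wait, if events fall at random between meetings: L / 2 = 13.0 weeks.
- Share of 24-week courses containing no meeting: 1 − 24/26.1 = 8%.
- Non-serious EKG finding at Week 4, chance of no meeting before that subject reaches Week 24: 1 − 20/26.1 = 23%.
- The same at Week 12: 1 − 12/26.1 = 54%.

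These shares assume that meeting dates are unrelated to a subject's start date.

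**3. Number of meetings.** Section 12.1 expects 25 subjects to enrol and complete within 1 year. With 12 / 6 = 2 intervals, there may be only about one meeting while subjects are still under treatment, if that timetable holds and the first meeting comes about 6 months after the start.

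**4. Is the event foreseeable?** Section 6.4 gives the cited study's arms as "n=10 clenbuterol, n=9 placebo", while Table 1 gives "19 subjects -- 10 placebo 9 clenbuterol". The two disagree, so both denominators are carried.
- Ventricular tachycardia leading to discontinuation: 1/10 = 10% (exact 95% interval 0.3% to 44.5%) or 1/9 = 11% (0.3% to 48.2%).
- Chance of at least one such event in 25 subjects is 1 − (1 − p)^25. At assumed true rates of 1%, 2% and 5% this is 22%, 40% and 72%.

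The interval is too wide, and the population too different, for the cited rate to serve as an estimate here. It shows only that the event can be foreseen from the protocol's own background. These chances concern occurrence; they do not say how often such an event would be detected or graded non-serious.

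**The case against.** The strongest reply is that section 13.1.2 already covers the case. A ventricular arrhythmia can be judged an important medical event, becomes an SAE, and reaches the Chair within a day. That is possible, but it rests on judgement, and the examples given do not include arrhythmia. It also does not help with other adverse events that stop the drug.

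A reader might infer more from section 6.4: that by placing a ventricular tachycardia beside a statement of no serious events, the protocol has ruled such events non-serious, so the same event here would miss the fast route. The documents do not support this. Section 6.4 summarises another study and sets no grading rule; seriousness here is governed by section 13.1.2. Nor is section 6.4 shown to be wrong. Discontinuation is not a seriousness criterion, and an asymptomatic slow tachycardia can be non-serious. Nothing is hidden either: section 6.4 and Table 1 both name the tachycardia as a reason for stopping.

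A reader might also scale the cited study's two discontinuations to this trial, 25 × 2/10 = 5 subjects. That would mix a cramps withdrawal into an arrhythmia argument, rest on 9 or 10 heart-failure subjects, and assume every such stop is graded non-serious. Section 9.2 here excludes clinically relevant EKG abnormality, including arrhythmia and cardiomyopathy, and the Table 1 entries for the ALS pilot and the Pompe study list no arrhythmia. The figure should not be used.

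Finally, it is fair to say that 26 weeks is a maximum, that the investigator is not waiting for the DSMB, and that section 13.6.1 contradicts nothing. All of that stands. The point is an improvement to oversight rather than the correction of an error.

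**Conclusion.** The point holds as a gap in section 13.6.1 read with sections 13.1.1 and 13.1.2. A ventricular arrhythmia, or any adverse event that stops study drug, has no prompt route to the DSMB if it is graded non-serious. The wait is at most about 26 weeks and about 13 on average, against 24 weeks of treatment. The average and the 23% and 54% figures assume random timing relative to meetings; the maximum assumes that meetings keep to the stated interval. The conclusion needs no assumed event rate. It is conditional on the grade: an event graded serious goes to the Chair within 24 hours as the plan stands. It concerns DSMB review only, and it is a worthwhile, inexpensive change in a trial whose primary endpoint is safety.

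**What to change.** In section 13.6.1, add to the 24-hour notice to the DSMB Chair, regardless of seriousness grade: (a) any ventricular arrhythmia, and (b) any adverse event leading to discontinuation of study drug.

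This alters reporting only, not dosing or the management of subjects. It costs one sentence and a few notices, some about events that prove minor. Notice of every dose reduction is not proposed: section 6.4 mentions reductions for minor events in the Pompe study, and the added burden is hard to justify. No rewrite of section 6.4 is needed for this point.

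One limit remains. The change speeds notice of events that are found. The cited tachycardia was seen on a 24-hour recording, whereas section 11 lists an EKG at visits only, so an asymptomatic episode between visits might not be seen.
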